6.6 Skin Assessments and Procedures

All subjects will be evaluated using the Skin Irritation Scale:

Inflammatory Responses:

0	=	No visible reaction
+	=	Slight, confluent or patchy erythema
1	=	Mild erythema (pink)
2	=	Moderate erythema (definite redness)
3	=	Strong erythema (very intense redness)

Definition of letter grades appended to a numerical grade:

E	=	Edema - swelling, spongy feeling when palpated
P	=	Papule - red, solid, pinpoint elevation
V	=	Vesicle - small elevation containing fluid
B	=	Bulla reaction - fluid-filled lesion (blister)
S	=	Spreading - evidence of the reaction beyond the Webril pad area
W	=	Weeping - result of a vesicular or bulla reaction - serous exudate
I	=	Induration - solid, elevated, hardened, thickened skin

Superficial Effects

g	=	Glazing
y	=	Peeling
c	=	Scab, dried film of serous exudate of vesicular or bulla reaction
d	=	Hyperpigmentation (reddish-brown discoloration of test site)
h	=	Hypopigmentation (loss of visible pigmentation at test site)
f	=	Fissuring grooves in the superficial layers of the skin

All skin responses observed during the induction and challenge phases will be reported. Skin responses to each patch application will be examined and graded under light supplied by a 100-watt incandescent blue bulb. The evaluator and Investigator will be blinded to treatment assignment and any previous scores. The same individual will conduct all skin evaluations of the test sites, but a qualified back-up individual will be available if needed.

Individual investigational products during the induction phase will be applied to the assigned skin site unless the site reactions become so strong as to make it inadvisable. If excessive irritation, (for example, a numerical score of 2 or greater or any grade (even 0) if appended with a letter grade of E, P, V or B) is noted, that site will be discontinued from further patching and a new site adjacent to the original site will be used for the remainder of the required applications. If excessive irritation occurs at the move site, a second move site may be used. Excessive irritation at the second move site would require discontinuation of that patch material.

The challenge patches will be applied to naïve sites on the opposite side of the back for approximately 48 hours. Challenge sites will be evaluated approximately 30 minutes, 24 (± 1), 48 (± 2) and 72 (± 2) hours after patch removal. Evaluation of the test articles for the potential to sensitize should include a review of the induction site scores as well as the challenge site scores and a narrative description of any reaction observed at challenge will be recorded. The opinion from the investigator as to whether the reaction is indicative of contact sensitization will be documented in the study records and reported in the final report.

Photos will be taken of any reactions of concern and will be shared with the sponsor but will not be part of the final report.

6.7 Randomization and/or Treatment Assignment

To eliminate any position bias, the assignment of the test product code to the test sites will be randomized among the subjects so that each test product code occupies individual skin sites within the panel of test subjects with equal frequency.

6.8 Assessment of Sensitization

Subjects who had all 9 induction patches and completed the challenge phase (at least the 24-hour post challenge skin assessment) will be considered evaluable subjects for the study. The Principal Investigator in consultation with the irritation grader will review all induction and challenge scores recorded for all evaluable subjects. The induction of dermal sensitization is determined by enhancement of the skin reaction observed at Challenge greater than that observed during Induction. Low grade reactions observed during Induction, but which are not observed at Challenge are considered to be irritant in nature.

An erythematous and edematous reaction to the test article (and none to the negative control) during Challenge is indicative of dermal sensitization. Usually the skin irritation score response is greater than scores observed during induction phase and often spreads outside of the patch site. If sensitization is suspected, a full description of the skin responses observed will be documented and reported in the final report.

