4.4 Administration of Test Products

For all subjects, the test products will be placed, on Webril patch pads (2 x 2 cm) adhered to occlusive tape (approximately 4 x 4 cm) and will be applied as per study design and randomization scheme onto designated sites located on the back of each subject unless the skin condition becomes sufficiently irritated to require a change to a semi-occlusive tape or even an open dressing, at the discretion of the investigator.

The patches will be reinforced with additional non-irritating tape as deemed necessary by the patch applicator. Subjects will be instructed to keep all patches dry during showering so that the test sites are protected from accidental water exposure for the duration of the study.

Two test sites located on one side of the paraspinal region of the back will be utilized for application. The assignment of the test product codes to individual skin sites will be randomized so that each test product code occupies individual skin sites within the panel of test subjects, with approximately equal frequency, in order to eliminate any position bias. The sites of patch/test product application will be marked by a skin marker so that the location of the patch pad/application site is clearly indicated for evaluations.

The test products will be applied and removed by study personnel. The study will involve repetitive and continuous patch applications of all investigational products, Codes A and B, approximately 48 hours on weekdays and for approximately 72-hour periods over weekends over 3 weeks, for a total of 9 induction applications. All applications for individual test products will be made to the same site unless reactions become so strong as to make this inadvisable. If excessive irritation, (for example, a numerical score of 2 or greater) is noted, that site will be discontinued from further patching and a new site adjacent to the original site will be used for the remainder of the required applications (move site 1). If excessive irritation occurs at the move site, a second move site may be used. Excessive irritation at the second move site would require discontinuation of that patch. Residue on the skin from any test patch will be removed by study staff prior to skin evaluation (if observed) by gently wiping the patch application site with a moistened gauze pad.

Photos will be taken of any reactions of concern and will be shared with the sponsor but will not be part of the final report.

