5.5 Challenge Phase (Visit 11)

- Adverse event, concomitant medication review
- Eligibility review
- Patch application

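### Section 6.8's nine-patch rule takes subjects stopped or withdrawn for a skin reaction out of the evaluable count and the sensitization review

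*Combined protocol and SAP*

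**What the plan says.** Section 6.8 of the protocol sets the evaluable population: "Subjects who had all 9 induction patches and completed the challenge phase (at least the 24-hour post challenge skin assessment) will be considered evaluable". The investigator, consulting the grader, "will review all induction and challenge scores recorded for all evaluable subjects". Two criteria follow. One is a challenge reaction stronger than those seen in induction. The other is: "An erythematous and edematous reaction to the test article (and none to the negative control) during Challenge is indicative of dermal sensitization". Low-grade induction reactions that do not recur at challenge are called irritant.

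The stopping rule is in the synopsis and in sections 4.4 and 6.6. After excessive irritation the patch moves to an adjacent site, and a second move is permitted. Section 6.6 then states: "Excessive irritation at the second move site would require discontinuation of that patch material". The examples of excessive irritation in 6.6 are a score of 2 or more, or any score, even 0, carrying the letter for edema, papule, vesicle or bulla. Section 3.3 separately allows removal of a subject for intolerance, or on the investigator's judgement.

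On challenge, the synopsis and section 2.1 describe challenge applications of each product after the rest period, with no exception. Section 5.5 lists an "Eligibility review" at Visit 11 before the challenge patch, but section 6.2 describes eligibility review only at Visit 1 and before randomization.

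**The concern.** The primary objective is the product's potential to sensitize. Under 6.8, membership in the set reviewed for that objective depends partly on the reaction being studied, because a strong enough reaction during induction ends patching, and a subject without nine patches is not evaluable. The overlap is direct. Edema is among the signs that 6.6 treats as excessive, and edema with erythema is the sign that 6.8 takes as indicating sensitization at challenge. A subject who becomes sensitized during induction is therefore among those whom the rule can remove.

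At stake is the meaning of a finding such as no cases among the evaluable subjects. The protocol plans about 60 subjects with 50 completing and no replacement, and it does not separate losses caused by skin reactions from other losses. A count limited to evaluable subjects would leave reaction-stopped subjects outside it, without a classification under 6.8.

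**Working it through.** **1. The plan's own figure.** There is none to reproduce. The synopsis says that the sample size was not calculated, and section 7.2 plans tables without statistical analysis. The implied allowance for loss is 60 − 50 = 10 subjects (10/60 = 16.7%), for any cause.

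**2. What happens to each kind of reactor under the text.**

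| Subject | Nine test-product patches? | In the 6.8 review? | What other text provides |
|---|---|---|---|
| Reacts, moves site, continues to patch 9, completes challenge | Yes | Yes | Full review |
| Stopped before patch 9, challenged, reacts | No | No | 6.6 narrative and investigator opinion |
| Stopped before patch 9, challenged, no reaction | No | No | Scores reported |
| Stopped before patch 9, not challenged | No | No | Induction scores reported; no criterion in 6.8 applies |
| Withdrawn for a skin reaction before patch 9 | No | No | Scores reported; adverse event under 8.1 |

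The second row is decisive. Even a stopped subject with a clear positive challenge fails the nine-patch condition. In the last two rows neither criterion in 6.8 can be met, since both need a challenge reading. The irritant default covers only low-grade induction reactions, so it does not fit someone stopped for excessive irritation. The protocol does not say that the nine patches are counted per product. The table takes the natural reading, that a subject stopped on the test product has not had all nine.

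**3. When a stop can occur.** Sections 4.4 and 6.6 permit a second move site but do not require it. If it is used, the mandatory stop follows the third excessive reading. If it is not used, stopping can follow the second. Withdrawal under 3.3 needs no particular number of readings. No minimum patch count and no latest day can therefore be derived, and nor can the number of subjects affected.

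**4. Illustration of scale.** Let k be the number stopped for a reaction to the test product and not classified. The documents give no value, so k = 1, 2, 3 is assumed. With no case among 50 evaluable subjects, counting all k as possible cases gives k/(50 + k). The exact (Clopper-Pearson) one-sided 95% upper limit is the 0.95 quantile of a beta distribution with parameters k + 1 and 50. For k = 0 this is 1 − 0.05^(1/50) = 5.8%.

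| k (assumed) | Count | Proportion | One-sided 95% upper limit |
|---|---|---|---|
| 0 | 0/50 | 0% | 5.8% |
| 1 | 1/51 | 2.0% | 9.0% |
| 2 | 2/52 | 3.8% | 11.6% |
| 3 | 3/53 | 5.7% | 14.0% |

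Under the rule as written, the evaluable result is 0/50 in every row. The other figures are outer limits, because some stopped subjects will have had irritant reactions.

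**The case against.** The best defence is that little is hidden. Section 6.6 says that all skin responses in both phases are reported, without restriction to evaluable subjects. Section 7.2 tabulates the individual site data, and 8.1 makes irritation that leads to withdrawal an adverse event. Stopping a product is not listed in 3.3 as a reason for withdrawal, and the stopping rule sits in text about the induction phase. On the default reading of the synopsis and 2.1, the subject stays in the study and is challenged. Section 6.6 then applies: "a narrative description of any reaction observed at challenge will be recorded", with a reported investigator opinion, again not limited to evaluable subjects. The last sentence of 6.8 (a full description if sensitization is suspected) and the determination required by 13.1 name no population. The move sites, and the allowance in 4.4 for skin "sufficiently irritated to require a change to a semi-occlusive tape or even an open dressing", help to keep reactors on patching to the ninth application.

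All of this stands, and it rules out two stronger readings. A reader might infer that stopped subjects vanish from the report; the reporting provisions show otherwise. A reader might also infer that they are never challenged; the general design text points the other way, although nothing says explicitly that a stopped product is challenged and Visit 11 gives no criterion. What the defence does not reach is 6.8 itself. The reported scores are not classified under its criteria, and a challenged subject with fewer than nine patches is still outside the evaluable set and its score review.

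**Conclusion.** The concern holds as a defect in who is counted and reviewed for sensitization. The direction of the bias in the evaluable result is clear: toward no sensitization. Its size is unknown. The 0/50 to 3/53 range rests on an assumed k, on exactly 50 evaluable subjects with no case, and on treating every stopped subject as a possible case. The protocol plans no inference, so the limits only show scale. A reader might infer from them that the true sensitization rate would be understated by a known amount; the documents give no rate of stopping and no share of stopped subjects who are sensitized, so they do not support that. The point should be fixed because the wording defeats part of its purpose and the repair is cheap, but it does not invalidate the study.

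**What to change.** Amend section 6.8, with a matching line at Visit 11:

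- (a) Require nine patches only for counting a subject as negative.
- (b) Keep in the sensitization review every subject whose product was stopped, or who was withdrawn, for a skin reaction.
- (c) Challenge these subjects on naive skin where the investigator judges it safe, and say so in the Visit 11 eligibility review. Count a positive challenge as positive under the existing 6.8 criteria, applied alike to all subjects.
- (d) Report those not challenged in a separate row, *stopped for reaction, indeterminate*, with a sensitivity count that treats them as possible cases.

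The cost is a short protocol amendment with IRB review, possibly a consent line on challenge after a strong reaction, and one table row. The drawback is that the sensitivity row may include irritant reactions, so it should be labelled as an outer limit. Whether to challenge a strong reactor remains the investigator's safety decision.

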7 STATISTICAL METHODS

7.1 Randomization

A computer-generated randomization scheme will be used to obtain a balanced allocation of each test code to each treatment site.

7.2 Statistical Analysis

Data from the individual patch sites will be presented tabular format. No statistical analysis of the data will be performed.

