skin site unless the site reactions become so strong as to make it inadvisable. If excessive irritation, (for example, a numerical score of 2 or greater) is noted, that site will be discontinued from further patching and a new site adjacent to the original site will be used for the remainder of the required applications. If excessive irritation occurs at the move site, a second move site may be used. Excessive irritation at the second move site would require discontinuation of that investigational product.

The challenge patches will be applied to naïve sites on the opposite side of the back for approximately 48 hours. Challenge sites will be evaluated approximately 30 minutes, 24 (± 1), 48 (± 2) and 72 (± 2) hours after patch removal. Evaluation of the test articles for the potential to sensitize should include the site scores as well as a narrative description of any reaction and an opinion from the investigator as to whether the reaction is indicative of a contact sensitization.

Photos will be taken of any reactions of concern and will be shared with the sponsor but will not be part of the final report.

SAFETY ASSESSMENTS:

Safety will be assessed by monitoring of adverse events reported during the study.

STATISTICAL ANALYSES:

Data from the individual patch sites is presented in tabular format. No statistical analysis of the data will be performed.

SAMPLE SIZE DETERMINATION:

Based on prior experience with contact sensitization studies in humans approximately 60 subjects will be randomized to ensure 50 subjects completing the study. There is no statistical calculation of sample size for this study.

SITES:

This study will be conducted at 1 site located in the United States.

SPONSOR:

Omeza

TABLE OF CONTENTS

1	INTRODUCTION, RATIONALE, AND OBJECTIVES.....	10
1.1	Introduction.....	10
1.2	Rationale.....	10
1.3	Objectives.....	10
2	INVESTIGATIONAL PLAN.....	11
2.1	Overall Study Design	11
2.2	Randomization and Blinding Procedure	11
3	SELECTION AND WITHDRAWAL OF SUBJECTS	11
3.1	Inclusion Criteria.....	11
3.2	Exclusion Criteria.....	12
3.3	Subject Withdrawal Criteria	12
4	STUDY TREATMENTS	13
4.1	Identity of Test Products.....	13
4.2	Test Product Storage and Accountability.....	13
4.3	Methods of Assigning Subjects to Treatment Groups.....	13
4.4	Administration of Test Products.....	14
4.5	Treatment Accountability and Compliance	14
4.6	Blinding and Unblinding Method.....	14
5	SCHEDULE OF PROCEDURES AND ASSESSMENTS	14

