1 INTRODUCTION, RATIONALE, AND OBJECTIVES

1.1 Introduction

1.2 Rationale

This study design has been selected by the sponsor to address comments provided by the FDA in order to aid in identifying and eliminating any potential irritants or sensitization in future product development and is based on a Modified Draize Human Repeat Insult Patch Test design. The Modified Draize Procedure¹ is used as a predictive test for contact sensitization in humans. The procedure involves the application of a discontinuous series of multiple occlusive patches to human skin over a three-week induction period. Induction is followed by an approximate two-week rest period. Challenge consists of a single application to naive skin.

¹Marzulli, F.N. and Maibach, H.I. (1977) Contact Allergy: Predictive Testing in Humans. In Advances in Modern Toxicology.

Dermatotoxicology and Pharmacology. Eds. Marzulli, F.N and Maibach, H.I. 4, 353-372.

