13 REPORT

13.1 Final Report

The final report will summarize the method and adverse events relative to the test product and the subjects. A determination of the test product's potential for sensitization, including any necessary discussion, will be included in the report. A demographics table with subject numbers, age, race and gender will be provided as an Appendix in the report.

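### The report must give a determination of sensitization potential, but nothing requires it to state what about 50 evaluable subjects can exclude, or to count beside it subjects lost because a product was stopped for irritation

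*Combined protocol and SAP*

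**What the plan says.** **Analysis.** Section 7.2 reads: "Data from the individual patch sites will be presented tabular format. No statistical analysis of the data will be performed". The synopsis, under Statistical Analyses, agrees: "Data from the individual patch sites is presented in tabular format. No statistical analysis of the data will be performed". Section 12.2 adds only that the statistician provides tables and score frequencies.

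**Conclusion required.** Section 13.1 says that a determination of the test product's "potential for sensitization, including any necessary discussion, will be included in the report". Section 1.2 gives the context: "This study design has been selected by the sponsor to address comments provided by the FDA".

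**Sample size.** From prior experience and without a calculation, "approximately 60 subjects will be randomized to ensure 50 subjects completing the study" (synopsis, Sample Size Determination). Withdrawn subjects are not replaced (sections 3 and 4.3).

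**Who is judged.** Section 6.8 defines the evaluable set as "Subjects who had all 9 induction patches and completed the challenge phase", where completing challenge means at least the 24-hour reading. The investigator, with the grader, "will review all induction and challenge scores recorded for all evaluable subjects".

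**How a product is stopped.** An excessively irritated site is abandoned for an adjacent one, and a second move is allowed. The synopsis continues: "Excessive irritation at the second move site would require discontinuation of that investigational product". Sections 4.4 and 6.6 have equivalent rules.

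**What is reported in any case.** The synopsis and section 6.6 have all skin responses in both phases reported. Section 6.6 also has any challenge reaction described in a narrative, and the investigator's opinion on contact sensitization given in the final report. Neither provision is restricted to evaluable subjects. Under section 8.1, irritation is an adverse event only if it leads to withdrawal from the study.

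**The concern.** There are two gaps, and both concern what stands next to the conclusion.

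First, the plan ends in a determination but attaches no measure of uncertainty to it. Zero cases in about 50 people can easily be read as evidence that the product does not sensitize. In fact it excludes only panel rates above a limit that the report need not state.

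Second, the evaluable denominator depends on the reactions themselves. Subjects whose product is stopped before the ninth patch are those with the strongest induction responses, and they fall outside the set that section 6.8 directs the investigator to review. The adverse event summary need not catch them either, because stopping one product is not withdrawal from the study. A reader could see a clean result in the evaluable set without seeing, in the same place, that some strong reactors are not in it.

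**Working it through.** **Inputs.** About 60 randomized and 50 completing (synopsis). Evaluable means all 9 induction patches plus at least the 24-hour challenge reading (section 6.8). No error rate, assumed sensitization rate, margin or dropout rate is given. Assumptions made here: a 95% confidence level, and 1 to 5 subjects stopped for irritation, used only for illustration.

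**The plan's own figure.** 60 and 50 imply 10/60 = 16.7% non-completion. The documents do not state this rate and disclaim any calculation, so there is nothing to reproduce. The target of 50 counts completers. The evaluable set also needs all 9 patches, so it can be smaller.

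**What a clean result excludes.** With 0 cases in n, the exact upper limit is 1 − 0.025^(1/n) two-sided and 1 − 0.05^(1/n) one-sided.

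| Result | Two-sided 95% | One-sided 95% |
|---|---|---|
| 0/45 | 7.9% | 6.4% |
| 0/50 | 7.1% | 5.8% |
| 0/55 | 6.5% | 5.3% |
| 0/60 | 6.0% | 4.9% |

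The probability of no cases in 50 at an assumed true panel rate p is (1 − p)^50. At 2% it is 0.98^50 = 0.364. At 5% it is 0.95^50 = 0.077.

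**How a subject leaves the denominator.** A stop needs excessive irritation at the original site, the first move site and the second move site.

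- Earliest: the readings after applications 1, 2 and 3 are all excessive. The product stops with six applications left.
- Latest that matters: the third excessive reading follows application 8, so only the ninth patch is missed.
- Either way the subject has not had all 9 patches of that product and is not evaluable under section 6.8.

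**Effect on the result, for 1 to 5 assumed matrix stops.**

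- *Stops come out of the 50:* the result is 0/49 to 0/45, with a two-sided upper limit of 7.3% to 7.9%.
- *50 evaluable are still reached; stopped subjects are added to the denominator, all challenged and all judged negative:* 0/51 to 0/55, upper limit 7.0% to 6.5%.
- *The same, but none has a challenge reading and all are counted as reactors:*

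| Result | Proportion | Clopper-Pearson two-sided 95% |
|---|---|---|
| 1/51 | 2.0% | 0.05% to 10.4% |
| 2/52 | 3.8% | 0.5% to 13.2% |
| 3/53 | 5.7% | 1.2% to 15.7% |
| 4/54 | 7.4% | 2.1% to 17.9% |
| 5/55 | 9.1% | 3.0% to 20.0% |

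The last table is an outer bound. It treats unexamined subjects as sensitized.

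**The case against.** The determination is a case-by-case clinical judgement (sections 6.6 and 6.8) in a predictive patch test, not a planned estimate of a rate. Descriptive reporting is a legitimate choice, section 13.1 allows discussion, and a reader given the cases and the denominator can work out the bound. That stands against any claim that the missing hypothesis test is itself an error. It does not supply the interval: discussion is permitted, but no precision statement is required.

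A reader might infer that stopped subjects disappear from the report. The documents do not support that. All skin responses are reported, section 4.2 has every application and removal recorded, and the narrative and opinion required by section 6.6 would cover a challenge reaction in a non-evaluable subject. No section bars such subjects from challenge. Section 6.8 directs the review to evaluable subjects without forbidding a wider one. What remains is a matter of placement: no count or listing beside the determination.

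Stops may also be rare. They need excessive irritation at three sites, and the synopsis and section 4.4 allow a change to semi-occlusive tape or an open dressing, which may make them rarer.

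Finally, counting every stopped subject as a case would contradict section 6.8, which judges sensitization by the challenge response relative to induction. That is correct. A subject who was challenged must be classified on that result.

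**Conclusion.** The point holds as a minor reporting gap that is cheap to close. As written, the plan can produce a clean determination with no stated precision and a denominator that has lost its strongest reactors, with nothing beside the conclusion to show either.

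The first part does not depend on any stops: 0/50 leaves panel rates up to 7.1% (two-sided) or 5.8% (one-sided) unexcluded. The choice between the two is a convention, and the 95% level is an assumption. The second part depends on a number that the documents cannot give and that may be zero. If stops simply reduce the 50, the limit moves little, to 7.3–7.9% for 1 to 5 stops.

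Two stronger readings should be resisted. The 10.4% to 20.0% limits are not estimates of what the trial will show; they apply only if every assumed stopped subject lacks a challenge reading and is counted as a reactor. Nor can it be said that the regulator expected a precision statement: section 1.2 mentions FDA comments, but their content is not in the documents.

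**What to change.** In section 7.2 and in the synopsis (Statistical Analyses), replace the second sentence with:

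*No hypothesis test will be performed. The number and proportion of evaluable subjects judged sensitized will be given with an exact (Clopper-Pearson) two-sided 95% CI, and the upper limit will be quoted beside the determination in the final report. Beside it, the report will give the number of subjects not evaluable because a product was stopped for irritation, by product, with their grades and any challenge result. A sensitivity proportion will add all subjects whose matrix was stopped to the denominator. Those challenged will be classified by the investigator's judgement of their challenge result; only those with no challenge reading will be counted as reactors. This proportion will be labelled as an outer bound.*

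Carry the same content into section 13.1, so that the report specification matches. A paired matrix-against-saline table of challenge reactions is optional and is not needed to close either gap.

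The trigger for moving a site also differs. The synopsis and section 4.4 give a numerical score as their example, while section 6.6 adds certain letter grades at any score. These passages must be reconciled so that the counts have one definition.

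**Cost.** Text changes in three places, the reconciliation just described, and some extra tabulation of scores that already go to the statistician (section 12.2). No new assessments or visits are needed. The downside for the sponsor is that a clean result will be shown with an upper limit of about 6–8%.
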